## 8.3. Clinical Laboratory Tests

#### **8.3.1.** Laboratory Value Definitions

All laboratory assessments will be performed using a central laboratory except for urine pregnancy tests (as applicable). Laboratory values and change from baseline values will be summarized descriptively by visit. Baseline values will be determined using the nonmissing values collected before the first dose, prioritizing scheduled assessments over unscheduled visits. The last scheduled record before administration will be considered the baseline record. For baseline laboratory candidates with the same date and time in the same priority category, additional rules may be provided after consultation with the medical monitor to delineate which value will be defined as baseline.

#### **8.3.2.** Laboratory Value Summaries

Clinical laboratory tests, including hematology, serum chemistry, and urinalysis (refer to Table 5 of the Protocol), will be performed for each subject during the study in accordance with study schedule of assessments. If specific safety issues arise, additional unscheduled laboratory tests/analyses may be performed at the discretion of the investigator.

All test results and associated normal ranges from central laboratories will be reported in SI units. All tests with numeric values will have a unique unit per test.

Laboratory hematology and serum chemistry parameters identified in Table 5 of the Protocol will be summarized. Numeric laboratory values will be summarized descriptively in SI units, and non-numeric test values will be tabulated when necessary. In addition, box-and-whisker plots will be provided for lab parameters if applicable.

For test results that will be summarized with available normal ranges, the number and percentage of subjects with the laboratory values being low, normal, high, and missing will be tabulated by each test and each visit.

A listing of abnormal laboratory values will be provided.

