If a subject has vitiligo present on more than 20% of BSA, the application of study drug will be limited to $\leq 20\%$ of the subject's total BSA and areas treated at baseline should continue to receive treatment until the end of the double-blind period (Week 52) unless the subject meets criteria for stopping study drug because of an AE.

Reference Therapy, Dosage, and Mode of Administration: Vehicle cream is matching in appearance to INCB018424 cream and is to be applied in the same manner as INCB018424 cream.

Study Schedule/Procedures:

Study visits are as follows:

Screening: Up to 28 days before enrollment. Screening will begin at the time that the subject signs the informed consent and will continue until the date the subject is enrolled in the study (Day 1).

Vehicle-controlled, double-blind treatment: Subjects will have study visits on Day 1 and at Weeks 4, 8, 12, 18, and 24 for assessment of safety and efficacy.

Continued double-blind treatment: Subjects will have study visits at Weeks 28, 34, 40, 46, and 52 for assessment of safety and efficacy.

Open-label extension: Subjects will have visits at Weeks 56, 68, 80, 92, 104, 116, 128, 140, and 156 for assessment of safety and efficacy.

On the day of a visit, subjects should not apply the study drug at home and will apply the next dose of study drug from the new kit in the clinic. Subjects will be given a daily diary to record application times. Subjects will also be instructed to bring all study drug tubes with them to each visit so that compliance can be assessed.

Safety follow-up: Subjects will have follow-up assessments approximately 1, 3, and 6 months after the last dose of study drug to assess safety and efficacy. If prohibited treatment for vitiligo is started, then an earlier follow-up visit will be performed as a final, and thus end-of-study, visit.

Safety assessments:

At each scheduled study visit at the clinical site, targeted physical examinations, vital sign collection, laboratory assessments, collection of concomitant medications, and AE assessments will be performed.

Urinalysis and a 12-lead ECG will be performed at screening and end of treatment. All laboratory assessments will be performed using a central laboratory except for urine pregnancy tests. Toxicities will be monitored continuously and will be graded using the National Cancer Institute CTCAE v4.03 criteria.

Efficacy assessments:

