5.4.2. Criteria and Procedures for Dose Interruptions and Adjustments of Study Drug

In some circumstances, it may be necessary to temporarily interrupt treatment as a result of AEs or laboratory abnormalities that may have an unclear relationship to study drug. Except in cases of emergency, it is recommended that the investigator consult with the sponsor medical monitor (or other representative of the sponsor) before temporarily interrupting study drug. Additionally, the investigator must obtain approval from the sponsor before restarting study drug that was temporarily interrupted because of an AE or laboratory abnormality.

Individual subjects may have administration interrupted at the discretion of the investigator, in consultation with the sponsor, for AEs or laboratory abnormalities until these have resolved. Subjects **MUST** have administration interrupted in the following situations.

- The subject develops a Grade 2 increase in ALT ($> 3 \times \text{ULN}$) or AST ($> 3 \times \text{ULN}$); a Grade 2 decrease in ANC ($< 1.5 \times 10^9/\text{L}$) or platelets ($< 75 \times 10^9/\text{L}$); or a Grade 3 decrease in absolute lymphocyte count ($< 0.5 \times 10^9/\text{L}$). Laboratory abnormalities should be confirmed with repeat testing within 48 hours whenever possible and expedited delivery of the laboratory results requested.
- The subject develops a Grade 3 or higher laboratory abnormality, with the exceptions of lipase (in which case a Grade 4, $> 5 \times \text{ULN}$, results in discontinuation of study medication) or any asymptomatic triglyceride, cholesterol, or amylase elevations.

Laboratory abnormalities should be confirmed with repeat testing within a medically indicated timeframe, based upon the investigator's judgment and in collaboration with the sponsor's medical monitor, and expedited delivery of the laboratory results should be requested.

- The subject had a Grade 3 or 4 drug-related AE as determined by the investigator.

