9.4.2.2. Clinical Laboratory Tests

Laboratory test values outside the normal range will be assessed for severity based on the normal ranges for the clinical reference laboratory. The incidence of abnormal laboratory values will be tabulated.

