#### 5. STATISTICAL METHODOLOGY

## 5.1. General Methodology

Unless otherwise noted, SAS® software (SAS Institute Inc., Cary, NC; v9 or later) will be used for the generation of all tables, graphs, and statistical analyses. Descriptive summaries for continuous variables will include, but not be limited to, the number of observations, mean,

standard deviation, median, minimum, and maximum. Descriptive summaries for categorical variables will include the number and percentage of subjects in each category.

Interim analyses are planned for this study as defined in Section 9.

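### The Protocol promises a tabulated incidence of abnormal laboratory values, but the SAP specifies only by-visit summaries and a listing, with no per-subject ever-abnormal, worst-value or baseline-shift table

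*SAP*

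**What the plan says.** Protocol 9.4.2.2 makes two statements about laboratory data. The first concerns severity: "Laboratory test values outside the normal range will be assessed for severity based on the normal ranges for the clinical reference laboratory". The second is a commitment to a table: "The incidence of abnormal laboratory values will be tabulated".

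SAP 8.3 plans the following:

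- Numeric summaries: "Laboratory values and change from baseline values will be summarized descriptively by visit". Under SAP 5.1 the descriptive statistics include "standard deviation, median, minimum, and maximum". Box plots are added where applicable.
- Counts and percentages by category, where a test has reference limits: "the laboratory values being low, normal, high, and missing will be tabulated by each test and each visit".
- Abnormal values are also listed.

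SAP 8.3 mentions no count of subjects ever abnormal, no worst post-baseline value, no shift from baseline and no severity category for laboratory values. SAP 10.1 marks changes to Protocol-defined analyses as not applicable.

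Two other parts of the Protocol bear on this. Section 5.4.2 sets graded laboratory thresholds at which study drug must be interrupted, and asks for repeat tests: "Laboratory abnormalities should be confirmed with repeat testing within 48 hours whenever possible". Sections 8.1.1 and 8.2 count a laboratory abnormality as an adverse event only if it causes signs or symptoms, is judged clinically meaningful, needs therapy, or requires a change in study drug.

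**The concern.** A percentage low at each visit is a point prevalence. Incidence, in the sense a safety reader needs, is the number of subjects in a group who became abnormal at any time on treatment. The first does not determine the second, so the table the Protocol promises is not among the outputs SAP 8.3 specifies, and the difference is not declared.

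The question matters in this trial. Protocol 1.3 gives the haematological liabilities of systemic JAK inhibition as a reason for the topical route. Protocol 1.6.5 describes anaemia, thrombocytopenia and neutropenia with the oral drug as dose-related. Safety is a secondary objective of a dose-ranging study, and haematology is named in the safety endpoint. The natural summary is how many subjects per dose ever fell below normal, starting from what baseline, and how far.

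**Working it through.** The plan states no figure for this point, so there is nothing to reproduce. The check is a bound on incidence, followed by a comparison of texts.

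**Inputs.** About 30 subjects per group (Protocol Synopsis: 150 in five groups). Post-baseline visits in the vehicle-controlled period at Weeks 4, 8, 12, 18 and 24, so V = 5. The number low per visit, k, is not given in the documents. I assume k = 1 and also show k = 2. I also assume all 30 subjects are measured at every visit.

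**Bound.** If k of N subjects are low at each of V visits, the number ever low lies between k (the same subjects each time) and min(N, k × V) (different subjects each time).

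| k per visit | By-visit row | Fewest ever low | Most ever low, Weeks 4–24 |
|---|---|---|---|
| 1 | 1/30 = 3.3% | 1/30 = 3.3% | 1 × 5 = 5; 5/30 = 16.7% |
| 2 | 2/30 = 6.7% | 2/30 = 6.7% | 2 × 5 = 10; 10/30 = 33.3% |

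In either row the same by-visit table fits incidences that differ by up to a factor of 5. These are extremes, not expected values. They show that the table does not identify the quantity.

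**Baseline.** The by-visit categories do not separate a subject who enters low from one who becomes low. Protocol 3.2 admits haemoglobin down to 10 g/dL and platelets down to 100 × 10^9/L. If the laboratory's lower limits are above these cut-offs (an assumption; the documents do not give them), some subjects start in the low category. Planned change-from-baseline summaries show the average movement, not who crossed a limit.

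**Depth.** The low category puts a value just under the normal limit in the same cell as one below a Protocol 5.4.2 threshold, for example ANC below 1.5 × 10^9/L. The by-visit minimum shows the deepest value in a group at that visit, but not how many subjects reached a given depth.

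**Unscheduled values.** SAP 8.3.1 ranks scheduled above unscheduled records when choosing baseline. SAP 8.3.2 expects unscheduled tests, and Protocol 5.4.2 asks for repeats. Neither SAP section says whether such values enter the post-baseline tables.

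**Period.** After Week 24, vehicle subjects move to one of the three higher active regimens, and so do 0.15% QD subjects with less than 25% F-VASI improvement (Protocol 4.1). SAP 5.3.3 assigns the safety population to the treatment received on Day 1, and SAP 5.2 groups by the regimen initially assigned or received. A worst-value table over all 52 weeks on those groupings would therefore count values obtained on active drug under vehicle.

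**The case against.** The strongest reply is that the serious cases are already counted per subject. Under Protocol 5.4.2, specified falls in ANC, platelets and lymphocytes, specified rises in ALT or AST, and most Grade 3 or higher laboratory abnormalities require interruption. An abnormality that requires a change in study drug is an adverse event under Protocol 8.1.1. SAP 8.2.2 then tabulates TEAEs by maximum severity, Grade 3 or 4 events, and TEAEs leading to interruption. This stands, and it narrows the gap to milder abnormalities, those that never qualify as adverse events, and those present at baseline.

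Second, the SAP plans more than low/normal/high counts: by-visit minimum, maximum and change from baseline, box plots and a listing. With about 30 subjects per group someone could count from the listing. This also stands, but a listing is not the tabulation the Protocol promises.

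Third, Protocol 9.4.2.2 ties severity to the reference laboratory's normal ranges and promises a table only for incidence. The Synopsis sentence on CTCAE grading, "Toxicities will be monitored continuously and will be graded using the National Cancer Institute CTCAE v4.03 criteria", speaks of toxicities. So no CTCAE laboratory table was promised and then dropped. Grading is recommended here because it is informative.

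Fourth, the titles of the double-blind laboratory tables in SAP Appendix A cannot be read in this copy. The legible open-label laboratory tables are value summaries marked as standard, and the standard conventions are not available. The point therefore rests on the text of SAP 8.3, not on a claim about every table shell.

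Finally, the summary of changes for Protocol Amendment 1 says the laboratory section was shortened because some of its content did not apply to a topical study. That may explain a light approach, but the current Protocol keeps the incidence sentence, and the SAP was written to Amendment 1.

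**Conclusion.** The mismatch is real and modest. The Protocol promises a tabulated incidence of abnormal laboratory values; SAP 8.3 specifies outputs from which incidence cannot be derived without counting through a listing; and no departure is declared. On the assumed 1 of 30 low at each of five visits with complete data, the incidence to Week 24 could be anywhere from 3.3% to 16.7%. Dropout would change the denominators but not remove the ambiguity.

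Three stronger readings are tempting and not supported:

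- That cytopenia incidence and depth cannot be read from the planned output at all. Events forcing a drug change should be in the AE tables, and the deepest value per visit is in the numeric summaries.
- That unscheduled values are excluded. SAP 8.3.2 refers to each visit, while SAP 8.4 uses the term scheduled for vital signs. The laboratory section is silent, which is a gap and not an exclusion.
- That the range can be stretched to Week 52 for every group. With 10 visits the bound would be 1/30 (3.3%) to 10/30 (33.3%), but for vehicle and 0.15% QD that mixes treatments after Week 24.

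Nothing here touches the efficacy analyses.

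**What to change.** In SAP 8.3.2 add, by treatment group, a shift table from baseline to worst post-baseline category. Use the normal-range category for all tests that have ranges, and also CTCAE v4.03 grade for ANC, platelets, lymphocytes, haemoglobin, ALT and AST. The number of subjects newly abnormal can be read directly from it, which meets the Protocol commitment.

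Specify three things with it:

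- All scheduled and unscheduled values in the database count towards the worst value. Protocol 7.5.5 requires unscheduled local results to be recorded, with their reference ranges, when they lead to a dose change or when an extra test is done because of an AE; say how those are categorised.
- Day 1 to Week 24, including the Week 24 sample taken before any switch, is reported as the vehicle-controlled comparison.
- Weeks 24 to 52 are reported separately by treatment actually received after re-randomization, with the baseline for switched subjects stated.

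Keep the by-visit table as supportive. If the sponsor prefers not to add the table, SAP 10.1 should record the departure from Protocol 9.4.2.2. The cost is one or two extra tables from data already collected, with no new samples or visits.

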#### 8.4. Vital Signs

Values at each scheduled visit, change, and percentage change from baseline for vital signs, including systolic blood pressure, diastolic blood pressure, pulse, respiratory rate, and body temperature will be summarized descriptively.

Criteria for clinically notable vital sign abnormalities are defined in Table 4. The abnormal values for subjects exhibiting clinically notable vital sign abnormalities will be listed along with their assigned treatment group. Alert vital signs are defined as an absolute value outside the defined range and percentage change greater than 25%. The abnormal values for subjects exhibiting alert vital sign abnormalities will be listed.

Table 4: Criteria for Clinically Notable Vital Sign Abnormalities

Parameter	Raw Value	Percent Change From Baseline
Systolic blood pressure	< 90 or > 150 mmHg	< 25% or > 25%
Diastolic blood pressure	< 50 or > 90 mmHg	< 25% or > 25%
Pulse	< 45 or > 100 beats/min	< 25% or > 25%
Respiratory rate	< 8 or > 20 breaths/min	< 25% or > 25%
Body temperature	< 35.5°C or > 38.0°C	< 25% or > 25%

#### 9. INTERIM ANALYSES

An interim analysis will be conducted when at least half of the randomized subjects reach Week 12 and again at Week 24. The interim analyses will not include any stopping rules for futility or efficacy. There will be no external Data Monitoring Committee. Sites will remain blinded to study drug, but some personnel at Incyte without direct contact with sites will be unblinded. An internal committee will be charged with evaluating the unblinded efficacy and safety results in the interim analysis. As there are no plans for stopping early for efficacy, no adjustments of  $\alpha$  or final p-values for repeated testing are necessary.

For analysis of the primary endpoint, a cutoff for clinical data used in the first interim analysis will be based on the earliest date that the first 75 subjects complete the Week 12 visit or discontinue the study or study treatment. All visits occurring on or before this date for these 75 subjects will be included in the first interim analysis. The cutoff for the second interim analysis will be defined in a similar fashion.

#### 10. CHANGES AND MODIFICATIONS TO THE ANALYSIS PLAN

All versions of the SAP are listed in Table 5.

**Table 5:** Statistical Analysis Plan Versions

SAP Version	Date
Original	28 JUN 2017

## 10.1. Changes to Protocol-Defined Analyses

Not applicable.

## 10.2. Changes to the Statistical Analysis Plan

Not applicable.

## APPENDIX A. PLANNED TABLES, FIGURES, AND LISTINGS

This appendix provides a list of the planned tables, figures, and listings for the clinical study report. Standard tables will follow the conventions in the Standard Safety Tables initial version. In-text tables are identical in structure and content as appendix tables, but follow a Rich Text Format.

The lists of tables, figures, and listings are to be used as guidelines. Modifications of the list that do not otherwise affect the nature of the analysis will not warrant an amendment to the SAP.

#### **Tables for Double-Blind Period**

Table No.	Title	Population	Standard	In-Text		
Baseline and	Baseline and Demographic Characteristics					
1.1 Disposit	ion					
1.1.1.1	Analysis Populations	ITT	X			
1.1.1.2	Summary of Subject Disposition	ITT				
1.1.1.3	Summary of Number of Subjects Enrolled by Site	ITT	X			
1.2 Demogr	aphy			•		
1.1.2.1	Summary of Demographics	ITT	X			
1.3 Baseline	Characteristics					
1.1.3.1	Summary of Baseline Disease Characteristics	ITT				
1.1.3.2	Summary of Medical History	ITT	X			
1.4 Prior an	d Concomitant Medications					
1.1.4.1	Summary of Prior Medications	ITT	X			
1.1.4.2	Summary of Prior Medications for Vitiligo	ITT	X			
1.1.4.3	Summary of Concomitant Medications	ITT	X			
Efficacy						
2.1 F-VASI						
2.1.1.1	Summary of Subjects Achieving F-VASI50 Response at Week 24 (Primary Endpoint)	ITT				
2.1.1.2	Summary of Subjects Achieving F-VASI50 Response at Week 24	PP				
2.1.1.3	Summary of Subjects Achieving F-VASI50 Response by Visit From Baseline to Week 52	ITT				
2.1.1.4.1	Summary of Subjects Achieving F-VASI50 Response by Visit From Baseline to Week 52 and by Age ≤ 30 and > 30	ITT				

2.1.1.4.2	Summary of Subjects Achieving F-VASI50 Response by Visit From Baseline to Week 52 and by Categorical Baseline F-VASI Score	ITT	
2.1.1.4.3	Summary of Subjects Achieving F-VASI50 Response by Visit From Baseline to Week 52 and by Years Since First Onset of Vitiligo	ITT	

Table No.	Title	Population	Standard	In-Text
2.1.1.4.4	Summary of Subjects Achieving F-VASI50 Response by Visit From Baseline to Week 52 and by Skin Type	ITT		
2.1.1.4.5	Summary of Subjects Achieving F-VASI50 Response by Visit From Baseline to Week 52 and by Race	ITT		
2.1.1.5	Summary and Analysis of F-VASI Score by Visit From Baseline to Week 52	ITT		
2.1.1.6	Summary and Analysis of F-VASI Score by Visit From Baseline to Week 52 and by Age $\leq$ 30 and $>$ 30	ITT		
2.1.1.7	Summary and Analysis of F-VASI Score by Visit From Baseline to Week 52 and by Categorical Baseline F-VASI Score	ITT		
2.2 T-VASI	I			
2.1.2.1	Summary of Subjects Achieving T-VASI50 Response by Visit From Baseline to Week 52	ITT		
2.1.2.2.1	Summary of Subjects Achieving T-VASI50 Response by Visit From Baseline to Week 52 and by Age ≤ 30 and > 30	ITT		
2.1.2.2.2	Summary of Subjects Achieving T-VASI50 Response by Visit From Baseline to Week 52 and by Categorical Baseline F-VASI Score	ITT		
2.1.2.2.3	Summary of Subjects Achieving T-VASI50 Response by Visit From Baseline to Week 52 and by Years Since First Onset of Vitiligo	ITT		
2.1.2.2.4	Summary of Subjects Achieving T-VASI50 Response by Visit From Baseline to Week 52 and by Skin Type	ITT		
2.1.2.2.5	Summary of Subjects Achieving T-VASI50 Response by Visit From Baseline to Week 52 and by Race	ITT		
2.1.2.4	Summary and Analysis of T-VASI Score by Visit From Baseline to Week 52	ITT		
2.1.2.5	Summary and Analysis of T-VASI Score by Visit From Baseline to Week 52 and by Age $\leq$ 30 and $>$ 30	ITT		
2.1.2.6	Summary and Analysis of T-VASI Score by Visit From Baseline to Week 52 and by Categorical Baseline F-VASI Score	ITT		
2.3 F-PhGV	VA			
2.1.3.1	Summary of F-PhGVA by Visit From Baseline to Week 52	ITT		

2.1.3.2.1	Summary of F-PhGVA by Visit From Baseline to Week 52 and by Age ≤ 30 and > 30	ITT	
2.1.3.2.2	Summary of F-PhGVA by Visit From Baseline to Week 52 and by Categorical Baseline F-VASI Score	ITT	
2.1.3.2.3	Summary of F-PhGVA by Visit From Baseline to Week 52 and by Years Since First Onset of Vitiligo	ITT	
2.1.3.2.4	Summary of F-PhGVA by Visit From Baseline to Week 52 and by Skin Type	ITT	
2.1.3.2.5	Summary of F-PhGVA by Visit From Baseline to Week 52 and by Race	ITT	

TO LL M	TOTAL TOTAL	D 1.0	G. 1 1	T 75 4
Table No.	Title	Population	Standard	In-Text
2.4 T-PhGV	' A			
2.1.4.1	Summary of T-PhGVA by Visit From Baseline to Week 52	ITT		
2.5 F-PaGV	A			
2.1.5.1	Summary of F-PaGVA by Visit From Baseline to Week 52	ITT		
2.6 T-PaGV	A	1	!	l
2.1.6.1	Summary of T-PaGVA by Visit From Baseline to Week 52	ITT		
2.7 F-BSA			!	l
2.1.7.1	Summary of F-BSA by Visit From Baseline to Week 52	ITT		
2.8 T-BSA				
2.1.8.1	Summary of T-BSA by Visit From Baseline to Week 52	ITT		
2.9 VETF				
2.1.9.1	Summary of VETF by Visit From Baseline to Week 52	ITT		
2.10 PaGIC	-V			
2.1.10.1	Summary of PaGIC-V by Visit From Baseline to Week 52	ITT		
Safety				
3.1 Study D	rug Exposure			
3.1.1.1	Summary of Drug Compliance	Safety	X	
3.1.1.2	Summary of Study Drug Exposure	Safety	X	

3.2 Adverse	Events			
3.1.2.1	Overall Summary of Treatment-Emergent Adverse Events	Safety	X	
3.1.2.2	Summary of Treatment-Emergent Adverse Events by MedDRA System Organ Class and Preferred Term	Safety	X	
3.1.2.3	Summary of Treatment-Emergent Adverse Events by MedDRA Preferred Term in Decreasing Order of Frequency	Safety	X	
3.1.2.4	Summary of Treatment-Emergent Adverse Events by MedDRA System Organ Class, Preferred Term, and Maximum Severity	Safety	X	
3.1.2.5	Summary of Treatment-Related Adverse Events by MedDRA System Organ Class and Preferred Term	Safety	X	
3.1.2.6	Summary of Treatment-Related Adverse Events by MedDRA Preferred Term in Decreasing Order of Frequency	Safety	X	
3.1.2.7	Summary of Treatment-Related Adverse Events by MedDRA System Organ Class, Preferred Term, and Maximum Severity	Safety	X	
3.1.2.8	Summary of Grade 3 or 4 Treatment-Emergent Adverse Events by MedDRA System Organ Class and Preferred Term	Safety	X	
3.1.2.9	Summary of Grade 3 or 4 Treatment-Related TreatmentEmergent Adverse Events by MedDRA Preferred Term in the Open-Label Period	Safety	X	
Table No.	Title	Population	Standard	In-Text
3.1.2.10	Summary of TEAEs Leading to Death by MedDRA System Organ Class and Preferred Term	Safety	X	
3.1.2.11	Summary of Treatment-Emergent SAEs by MedDRA System Organ Class and Preferred Term	Safety	X	
3.1.2.12	Summary of Treatment-Emergent SAEs by MedDRA	Safety	X	
	Preferred Term in Descending Order of Frequency			
3.1.2.13	Preferred Term in Descending Order of Frequency  Summary of Treatment-Related SAEs by MedDRA System Organ Class and Preferred Term	Safety	X	
3.1.2.13	Summary of Treatment-Related SAEs by MedDRA System	Safety	X	
	Summary of Treatment-Related SAEs by MedDRA System Organ Class and Preferred Term Summary of TEAEs Leading to Dose Interruption by			
3.1.2.14	Summary of Treatment-Related SAEs by MedDRA System Organ Class and Preferred Term  Summary of TEAEs Leading to Dose Interruption by MedDRA System Organ Class and Preferred Term  Summary of TEAEs Leading to Discontinuation of Treatment by MedDRA System Organ Class and Preferred	Safety	X	
3.1.2.14	Summary of Treatment-Related SAEs by MedDRA System Organ Class and Preferred Term  Summary of TEAEs Leading to Dose Interruption by MedDRA System Organ Class and Preferred Term  Summary of TEAEs Leading to Discontinuation of Treatment by MedDRA System Organ Class and Preferred Term  Summary of Nonserious TEAEs by MedDRA System Organ Class and Preferred Term	Safety	X	
3.1.2.14 3.1.2.15 3.1.2.16 a	Summary of Treatment-Related SAEs by MedDRA System Organ Class and Preferred Term  Summary of TEAEs Leading to Dose Interruption by MedDRA System Organ Class and Preferred Term  Summary of TEAEs Leading to Discontinuation of Treatment by MedDRA System Organ Class and Preferred Term  Summary of Nonserious TEAEs by MedDRA System Organ Class and Preferred Term	Safety	X	

3.1.4.1	Summary of Systolic Blood Pressure	Safety	X	
3.1.4.2	Summary of Diastolic Blood Pressure	Safety	X	
3.1.4.3	Summary of Pulse	Safety	X	
3.1.4.4	Summary of Respiratory Rate	Safety	X	
3.1.4.5	Summary of Body Temperature	Safety	X	
3.1.4.6	Summary of Weight	Safety	X	

<sup>a Non-SAE table will be generated for the study with the express purpose of clinical trial results posting.

